Although rare, some adults display hypersensitivity to CBD. Participants with known hypersensitivity to CBD will be excluded from participating in Le Rêve 3.0. As noted above, some recent studies indicate that extremely high doses of CBD (much higher than what will be used in Le Rêve 3.0) might impair liver function. Therefore, as a precaution, study participants in Le Rêve 3.0 will be required to refrain from the use of any of the following contra-indicated drugs for at least one week prior to and for the duration of the study: erythromycin, clarithromycin, itraconazole, ketoconazole, posaconazole, voriconazole, ritonavir, telaprevir, boceprevir, amlodipine, gemfibrozil, cyclosporine, danazol, amiodarone, verapamil, diltiazem, rifampin, theophylline, tizanidine, bupropion, efavirenz, diflunisal, propofol, fenofibrate, lamotrigine, morphine, lorazepam, diazepam, clobazam, stiripentol, valproate, everolimus, sirolimus, or tacrolimus, and niacin (vitamin B3 greater than 1g/ day). Participants who cannot refrain from the intake of these contra-indicated drugs prior to and throughout the study will be excluded from participating in Le Rêve 3.0.

Defined CBD also contains low concentrations (1 mg each) of highly purified (>98%) forms of the terpenes linalool, myrcene, phytol, limonene,  $\alpha$ -terpinene,  $\alpha$ -terpineol,  $\alpha$ -pinene, and  $\beta$ -caryophyllene. Terpenes are widely used as fragrances and flavors in consumer products such as perfumes, cosmetics and cleaning products, as well as food and drink products. For example, the aroma and flavor of hops comes, in part, from sesquiterpenes (mainly  $\alpha$ -humulene and  $\beta$ -caryophyllene), which are used to make beer. Importantly, the terpenes in Defined CBD are designated by the FDA as GRAS (Generally Regarded as Safe) for oral consumption. Although rare, some adults display mild skin allergies to terpenes when applied topically. As a precaution, participants with known hypersensitivity to terpenes will be excluded from participating in Le Rêve 3.0.

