## 5.2 EXCLUSION CRITERIA

An individual who meets any of the following criteria will be excluded from participation in this study:

1) Self-reported body mass index > 32 calculated from patient's height (m) and weight (kg); weight (kg)/square height ( $m^2$ ).

2) Insomnia associated with clinically diagnosed sleep apnea (AHI greater than 15 events/hour), or movement disorders such as restless legs, periodic limb movement (PLM) (greater than 30 events/hour or greater than five events/hour with associated PLM arousals).

3) Are currently participating in a formal behavioral therapy program to facilitate sleep.

4) History of epilepsy or seizures.

5) History of liver disease.

6) Serious head injury or stroke within the past year.

7) Psychiatric disorders including major depression, bipolar, anxiety, or schizophrenia.

8) History of suicide attempt or current suicide ideation.

9) Evidence of any clinically significant, severe or unstable, acute or chronically progressive medical or surgical disorder (including planned medical procedures that may impact sleep), or any condition that may interfere with the absorption, metabolism, distribution, or excretion of the study drug.

10) Patients with a history of cardiovascular disease including poorly controlled hypertension, ischemic heart disease, arrhythmia, or severe heart failure.

- 11) Untreated metabolic disorder such as diabetes.
- 12) Medical conditions that result in frequent need to get out of bed (e.g. nocturia).
- 13) History of drug or alcohol abuse, including past or present history of cannabis dependence.
- 14) Inability to refrain from greater than two standard drinks/day of alcohol consumption for study duration.
- 15) Current cigarette smoker.
- 16) Currently chronic (daily) cannabis user.
- 17) Use of any substance with psychotropic effects or properties known to affect sleep/wake, including neuroleptics, morphine/opioid derivatives, antihistamines, stimulants, anti-depressants, clonidine, within one week prior to screening.
- 18) Use of any over-the-counter sleep medications including tryptophan, valerian root (*Valeriana officinalis*), kava (*Piper methysticum* Forst), melatonin, St John's Wort (*Hypericum perforatum*), Alluna (herbal sleep supplement with valerian root), and hemp within one week prior to screening.

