- 19) Inability to refrain from use of any of the following contra-indicated drugs for at least one week prior to and for the duration of the study: erythromycin, clarithromycin, itraconazole, ketoconazole, posaconazole, voriconazole, ritonavir, telaprevir, boceprevir, amlodipine, gemfibrozil, cyclosporine, danazol, amiodarone, verapamil, diltiazem, rifampin, theophylline, tizanidine, bupropion, efavirenz, diflunisal, propofol, fenofibrate, lamotrigine, morphine, lorazepam, diazepam, clobazam, stiripentol, valproate, everolimus, sirolimus, or tacrolimus, niacin (vitamin B3 greater than 1g/ day), grapefruit juice.
- 20) Consumption of xanthine-containing beverages (i.e., tea, coffee, energy drinks or cola) of more than five cups or glasses per day.
- 21) Inability to refrain from greater than 400mg/day of caffeine consumption for study duration.
- 22) Participation in any other clinical trial within 30 days before the screening visit.
- 23) Night shift workers (during the 12 months prior to the study and during the study).
- 24) Individuals who nap three or more times per week over the preceding month.
- 25) Current delayed sleep phase syndrome where wake-up time is regularly (>5x/week) later than 9:00 a.m.
- 26) Individuals having to travel across more than two time zones or outside of their country of residence at any time during the study.
- 27) Females who are pregnant, are planning to become pregnant, or are breastfeeding.

28) History of allergies particularly to plant-based products containing terpenes, i.e. flavors and aromatic natural oils for example citrus, mango, lavender, thyme, cedarwood and pine products.

29) Known hypersensitivity to cannabinoids, including CBD.

30) Individuals may be excluded from participating in the study based on the investigator's professional judgement.

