Although rare, some adults display hypersensitivity to CBD. Participants with known hypersensitivity to CBD will be excluded from participating in Le Rêve 3.0. As noted above, some recent studies indicate that extremely high doses of CBD (much higher than what will be used in Le Rêve 3.0) might impair liver function. Therefore, as a precaution, study participants in Le Rêve 3.0 will be required to refrain from the use of any of the following contra-indicated drugs for at least one week prior to and for the duration of the study: erythromycin, clarithromycin, itraconazole, ketoconazole, posaconazole, voriconazole, ritonavir, telaprevir, boceprevir, amlodipine, gemfibrozil, cyclosporine, danazol, amiodarone, verapamil, diltiazem, rifampin, theophylline, tizanidine, bupropion, efavirenz, diflunisal, propofol, fenofibrate, lamotrigine, morphine, lorazepam, diazepam, clobazam, stiripentol, valproate, everolimus, sirolimus, or tacrolimus, and niacin (vitamin B3 greater than 1g/ day). Participants who cannot refrain from the intake of these contra-indicated drugs prior to and throughout the study will be excluded from participating in Le Rêve 3.0.

Defined CBD also contains low concentrations (1 mg each) of highly purified (>98%) forms of the terpenes linalool, myrcene, phytol, limonene,  $\alpha$ -terpinene,  $\alpha$ -terpineol,  $\alpha$ -pinene, and  $\beta$ -caryophyllene. Terpenes are widely used as fragrances and flavors in consumer products such as perfumes, cosmetics and cleaning products, as well as food and drink products. For example, the aroma and flavor of hops comes, in part, from sesquiterpenes (mainly  $\alpha$ -humulene and  $\beta$ -caryophyllene), which are used to make beer. Importantly, the terpenes in Defined CBD are designated by the FDA as GRAS (Generally Regarded as Safe) for oral human consumption. Although rare, some adults display mild skin allergies to terpenes when applied topically. Participants with known hypersensitivity to terpenes will be excluded from participating in Le Rêve 3.0.

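### Exclusion 19 turns only on whether a person can refrain from a listed drug, so its text does not bar qualifying by stopping an ongoing prescription for at least 13 weeks; controlled hypertension is the clearest gap

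*Combined protocol and SAP*

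**What the plan says.** Criterion 19 in section 5.2 excludes on "Inability to refrain from use of any of the following contra-indicated drugs for at least one week prior to" and for the whole of the study. A list follows that includes amlodipine, verapamil and diltiazem.

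Section 2.3.1 gives the rule as a precaution connected with liver function: participants "will be required to refrain from the use of any of the following contra-indicated drugs". Section 8.2.4 repeats it and closes with the consequence: "Participants who cannot refrain from the intake of these contra-indicated drugs prior to and throughout the study will be excluded from participating".

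Three other criteria bear on who is left:

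- Criterion 9 excludes on "Evidence of any clinically significant, severe or unstable, acute or chronically progressive medical or surgical disorder", or on any condition that may interfere with handling of the study drug.
- Criterion 10 excludes "Patients with a history of cardiovascular disease including poorly controlled hypertension", and goes on to ischemic heart disease, arrhythmia and severe heart failure.
- Criterion 30 allows, but does not require, exclusion on the investigator's judgement.

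Section 6.5 (Concomitant Therapy) is marked not applicable. Section 1.3 lists medical history at screening. Section 5.4 describes a target population that self-identifies as eligible and is then pre-screened by an online survey and a scripted call.

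**The concern.** The test in criterion 19 is whether the person can do without the drug, not whether the person is being treated with it. That form suits a habit; criterion 14 uses it for alcohol ("Inability to refrain from greater than two standard drinks/day of alcohol consumption for study duration") and criterion 21 for caffeine. For a long-term prescription it leaves open who decides that the drug can be given up. A candidate who simply stops meets the literal rule. Nothing in the supplied text says that medical need excludes, that a prescribed drug must not be stopped in order to enrol, or that the prescriber must be involved.

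At stake is the safety of a participant who comes off a needed drug for the length of a home-based study. With blood pressure treatment, the loss of control may produce no symptom that the participant would report.

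**Working it through.** **Length of the stop.** Inputs are the schedule in section 1.3 and the participant duration in section 1.1.

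- On study: 2 (baseline) + 4 (treatment 1) + 1 (washout) + 4 (treatment 2) + 1 (washout) = 12 weeks. This reproduces the stated 12 weeks.
- Minimum time off a listed drug: 1 week before + 12 weeks on study = 13 weeks.
- If the week is counted back from the start of the four-week screening window: 1 + 4 + 12 = 17 weeks. Hence at least 13.

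**Size of the list.** Criterion 19 names 34 drugs, plus niacin above 1 g/day and grapefruit juice: 34 + 1 + 1 = 36 items. The hypertension example uses 3 of them (3/36 = 8%). This counts entries and does not measure risk.

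**Which users of listed drugs other criteria already remove.**

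| Criterion | What it removes | Stable hypertension controlled on a listed drug? |
|---|---|---|
| 4 | Epilepsy or seizures | No |
| 7 | Psychiatric disorders | No |
| 9 | Significant, severe, unstable or progressive disease | Arguable; a matter of judgement |
| 10 | Cardiovascular disease, with hypertension qualified as poorly controlled | Not clearly; the qualifier would serve no purpose if all hypertension were excluded |
| 17 | Recent use of psychotropic or sleep-affecting substances | No |
| 30 | Investigator's judgement | Possible, not required |

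Users of the lipid drugs on the list (gemfibrozil, fenofibrate, niacin) and of theophylline are not plainly covered elsewhere either. Hypertension is the clearest case because the protocol addresses it and stops at poor control.

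**What would detect harm.**

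- Section 10.1.7 has daily text messages to capture adverse events.
- Section 8.3.4 records worsening of a baseline condition as an adverse event.
- A medical monitor assesses events, and section 10.1.6 provides an independent safety monitor.

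These depend on someone noticing a change. None of the five rows in section 1.3 is a blood pressure reading. The vital signs that section 8.1 says can be derived from the wristband are heart rate, heart rate variability and respiratory rate.

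**The case against.** The strongest reply is that a person who medically needs amlodipine ordinarily cannot refrain from it, so criterion 19 already excludes that person. Sections 2.3.1 and 8.2.4 call the rule a precaution and end in exclusion, which fits that reading. It is reasonable and may be what was meant. But the term is undefined, and eligibility starts from self-identification, so the reading should be written down.

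A second reply is that medical history at screening, together with criteria 9, 10 and 30, gives the study team a route to see treated hypertension and exclude it. Criterion 9 is wider than severe or unstable disease, and the list in criterion 10 is inclusive. Some users of verapamil and diltiazem are already out through arrhythmia or ischemic heart disease. This narrows the gap. It does not close it, because nothing says what to do when such a prescription is found.

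A third reply is that the survey, call script and consent form are natural places for a warning not to stop prescribed medicines. They were not available, so the point is limited to the protocol text.

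Three stronger readings are tempting, and the documents do not support them:

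- A reader might infer that the protocol tells people to come off their treatment. It does not; it permits this by silence.
- A reader might infer that criterion 19 is an outlier because criteria 17 ("Use of any substance with psychotropic effects or properties known to affect sleep/wake") and 18 ("Use of any over-the-counter sleep medications including tryptophan") exclude on recent use. Both look back only one week before screening, so someone could also qualify under them by stopping in time. The contrast shows little.
- A reader might want the number of the 150 places at risk. The documents give no share of candidates taking a listed drug, and harm would further require that the person passes every screening step, stops, and is not moved to an unlisted alternative. No count can be defended.

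**Conclusion.** The point holds as a gap in wording with a safety consequence. Criterion 19 and its two repeats do not rule out qualifying by stopping an ongoing prescription, for at least 13 weeks. Hypertension controlled on one of three listed drugs is the clearest case that no other criterion plainly catches.

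Severity is low. The number of people concerned is unknown, a prescriber could substitute an unlisted drug without loss of control, and some oversight exists. The conclusion rests on three things: *inability* is not defined elsewhere to include medical need; the materials not seen do not already settle the matter; and amlodipine, verapamil and diltiazem are used for hypertension, which is general medical knowledge and not stated in the documents.

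**What to change.** In criterion 19, section 2.3.1 and section 8.2.4:

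- exclude anyone taking a listed drug as ongoing prescribed therapy at screening;
- state that no prescribed medicine may be stopped in order to qualify;
- keep the refrain wording for grapefruit juice, non-prescribed niacin and completed short courses.

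Someone whose own prescriber had already taken them off the drug for medical reasons would stay eligible. The medical monitor should settle the clinical detail. The survey, call script and consent form should be checked and matched to the new rule.

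The cost is a text change in three places, plus any participant materials that repeat the rule, with IRB review. An unknown, probably small, number of otherwise eligible candidates would be lost. The precaution about the listed drugs stays in force.

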Description of Sites/Facilities Enrolling Participants:	Le Rêve 3.0 will be a decentralized study completed by participants in the comfort of their own homes. Recruitment, enrollment, informed consent, and distribution of study materials to participants will all be managed by the contract research organization (CRO) 83 Bar, Inc.
Description of Study Interventions:	Study interventions will include Defined CBD or a placebo control that will be taken orally (p.o.) as two small capsules one hour prior to going to bed. Defined CBD is a capsule made to GMP standards composed of vegetable cellulose (gluten-free, non-GMO, vegan, certified kosher, certified halal) that contains 300 mg >99.9% purity hemp-derived CBD made in a GMP-certified laboratory that is dissolved in coconut oil (USDA certified organic, non-GMO, dairy-free, gluten-free, vegan coconut oil). Defined CBD is a custom chemical formulation that also contains low concentrations (1 mg each) of highly purified (>98% purity) forms of the terpenes linalool, myrcene, phytol, limonene, $\alpha$ -terpinene, $\alpha$ -terpineol, $\alpha$ -pinene, and $\beta$ -caryophyllene [Food Grade (GRAS), Natural, Organic, non-GMO, dairy-free, gluten-free, vegan] made in GMP-certified laboratories. Defined CBD contains no $\Delta$ -9-tetrahydrocannabinol ( $\Delta$ -9-THC). The safety of CBD  and these terpenes  at the doses found in Defined CBD is well established.
Study Duration:	The estimated time from when Le Rêve 3.0 opens enrollment until completion of data analyses will be 20 weeks.
Participant Duration:	After enrollment, the participant duration for the entire study will be 12 weeks.

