### 5.4 STRATEGIES FOR RECRUITMENT AND RETENTION

#### Recruitment Strategies

Participant recruitment and enrollment for Le Rêve 3.0 will be performed entirely by a CRO named 83Bar, Inc., who has extensive experience in managing all aspects of clinical trials. Recruitment materials will include (for details see Supplemental materials):

- Digital advertisements to appear on Facebook / Instagram and Google Search
- Landing pages
  - Landing page with embedded lead generation survey
  - Qualified results landing page
  - Not qualified results landing page
- Lead Generation Survey
- Emails
- Text messages
- Call script
- Privacy Policy
- Social Media Editorial Calendar
- Social Media Comment Moderation

**Design and Procedure:** Prospective candidates will see a digital ad on Facebook, Instagram, or Google search. After a prospective candidate clicks on the ad, they will be directed to a dedicated landing page that includes an embedded survey. The survey is designed to pre-screen prospective candidates. Survey respondents that are “survey qualified” will next receive a phone call from an 83bar Contact Center agent. If the prospective candidate answers the call, the agent will dialogue with the prospective candidate using an IRB-approved script (see supplemental materials). The script is designed to provide additional screening for prospective candidates. Interested participants will be provided with electronic consent forms. Information will then be sent to the study activation team for enrollment. Study candidates will also receive confirmation and reminder via email and text message. 83Bar predicts that upon receiving IRB-approval, the recruitment process will take approximately four weeks.

Target Population:

- Self-identify as meeting the study inclusion/exclusion criteria

Subject Recruitment:

- Potential candidates will be recruited from the general population using IRB-approved Facebook/Instagram and Google search advertisements. Potential candidates will complete an IRB-approved online pre-screening survey.
- Pre-screened potential candidates will be contacted by the 83bar Contact Center. The Contact Center will conduct verbal pre-screening using an IRB-approved script (see supplemental materials). If the candidate is interested in participating in the study, candidates that qualify based on online pre-screening and verbal pre-screening will be invited to participate in the study.

Participant Compensation:

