## 6 STUDY INTERVENTION

### 6.1 STUDY INTERVENTION(S) ADMINISTRATION

#### 6.1.1 STUDY INTERVENTION DESCRIPTION

Defined CBD is composed of small capsules made with vegetable cellulose (gluten-free, non-GMO, vegan, certified kosher, certified halal) that contain >99.9% purity hemp-derived CBD dissolved in coconut oil (USDA certified organic, non-GMO, dairy-free, gluten-free, vegan coconut oil) with a custom chemical formulation that also contains highly purified (>98% purity) forms of the terpenes linalool, myrcene, phytol, limonene,  $\alpha$ -terpinene,  $\alpha$ -terpineol,  $\alpha$ -pinene, and  $\beta$ -caryophyllene [Food Grade (GRAS), Natural, Organic, non-GMO, dairy-free, gluten-free, vegan]. Participants will be required to take two small capsules one hour before they go to bed. These capsules will contain a total of 300 mg CBD and 8 mg of terpenes (1 mg of each terpene). Defined CBD contains no  $\Delta$ -9-THC. The capsules that

contain the placebo control will look, feel and smell exactly the same as the capsules that contain Defined CBD, but will contain no CBD or terpenes.

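### The allergy exclusions (28 and 29) do not clearly cover coconut oil, the stated capsule vehicle, so a person with a known coconut allergy could meet the criteria as written

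*Combined protocol and SAP*

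**What the plan says.** **Composition.** Section 6.1.1 describes cellulose capsules holding "hemp-derived CBD dissolved in coconut oil", with eight terpenes. The synopsis (Section 1.1) likewise speaks of CBD "that is dissolved in coconut oil", and Section 8.2.2 repeats it. For the placebo, Section 6.1.1 says that it has neither CBD nor terpenes; it does not say what the vehicle is.

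**Exclusions (Section 5.2).** Exclusion 28 begins "History of allergies particularly to plant-based products containing terpenes" and goes on to specify flavors and aromatic oils, with six examples, citrus, mango and pine among them. Exclusion 29 is "Known hypersensitivity to cannabinoids, including CBD". Exclusion 30 leaves room for the investigator's judgement. None of the three mentions coconut or excipients.

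**Stated reasons.** Section 2.3.1 says that CBD-hypersensitive people are excluded. On terpenes it says: "As a precaution, participants with known hypersensitivity to terpenes will be excluded". Section 8.2.4 repeats both exclusions. Section 2.3.3 traces the trial's potential risks to CBD or terpenes. None of these sections mentions the vehicle.

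**Screening.** Under Section 5.4 the target population is people who "Self-identify as meeting the study inclusion/exclusion criteria". They pass through an online survey and then a scripted call. The schedule of activities (Section 1.3) also lists a medical history at screening.

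**The concern.** The protocol already treats known sensitivity to a capsule ingredient as a reason not to enroll someone. It does so for the terpenes, although Section 2.3.1 describes reactions to them as rare, mild and linked to topical use, and notes that they are recognized as safe for oral use. The oil that carries these ingredients is not addressed, and no reason is given for the difference.

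What is at stake is the safety of an individual participant in a decentralized trial where capsules are taken at home. Candidates are matched to the criteria largely on their own report, so the wording of the criteria carries more weight than it would with an on-site examination. Nothing here concerns the inference on deep and REM sleep.

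**Working it through.** No statistic is involved, so the check sets the composition beside the eligibility and risk text.

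| Listed component | Where stated | Exclusion that covers it | Reason given |
|---|---|---|---|
| CBD | 1.1, 6.1.1, 8.2.2 | 29 | 2.3.1 and 8.2.4: hypersensitive people excluded |
| Eight terpenes, 1 mg each (8 × 1 = 8 mg) | 1.1, 6.1.1, 6.1.2 | 28 | 2.3.1: excluded as a precaution |
| Coconut oil (vehicle) | 1.1, 6.1.1, 8.2.2 | None clearly | None; not mentioned in 2.3.1, 2.3.3 or 8.2.4 |
| Vegetable cellulose (shell) | 1.1, 6.1.1, 8.2.2 | None clearly | None |

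**Reading exclusion 28.** Two readings are possible.
- Broad: the opening words cover any allergy history and the rest is emphasis. Coconut allergy is then excluded, but so is every unrelated allergy, and no other section suggests that aim.
- Narrow: the clause after "History of allergies particularly to plant-based products containing terpenes" defines the scope as terpene-containing flavors and aromatic oils. Coconut is not among the examples. Sections 2.3.1 and 8.2.4, which speak of terpene sensitivity only, fit this reading.

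The narrow reading fits the rest of the protocol better, but the sentence is ambiguous.

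**Who is scheduled for exposure.** Under Section 4.1 every participant goes through both treatments, so everyone randomized is scheduled for the coconut-oil capsule, not just half the sample.
- Minimum nights in the active phase (Section 6.1.2): 4 nights/week × 4 weeks = 16.
- Maximum, from the pack supply (Section 6.2.2): 28.
- Placebo phase: cannot be determined, because the vehicle is not stated.

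These are scheduled nights. Someone who reacted might well stop, and Section 7.2 allows withdrawal at any point.

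**How many people.** With 150 enrolled, the expected number with a known coconut allergy would be 150 × p, before any who are caught by the medical history or decline after reading the consent form. The documents give neither p nor the share who would be caught, so no number follows.

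**The case against.** The best case for the plan has four parts.

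1. Exclusion 28 opens with a general allergy history, and its qualifier can be read as emphasis. This stands in part: the criterion is ambiguous rather than plainly silent. The ambiguity is itself a reason to edit it, since candidates and call agents have to apply it.
2. Other steps could catch the allergy: the medical history at screening, exclusion 30, a consent form that is to describe the intervention in detail (Section 10.1.1.1), and the explanation by a team member (Section 10.1.1.2). This stands as mitigation. But nothing in the protocol directs anyone to ask about excipients, so these steps work only if the allergy is volunteered or happens to be asked about.
3. The survey and call script are supplemental materials, and the consent form is a separate document. Any of them may name coconut or ask about food allergy. This stands in full and confines the point to the criteria as written. A reader might infer that candidates will not be asked, or that an allergic person will be dosed; the documents support neither.
4. The protocol nowhere promises to exclude allergy to every component, and it says nothing on how a coconut-allergic person would respond to this oil or how much oil a capsule holds. This also stands: the case rests on consistency with the protocol's own precaution on terpenes, not on a demonstrated hazard.

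**Conclusion.** The point holds in a limited form. The exclusions cover terpenes (28, ambiguously) and cannabinoids (29) and do not clearly cover the stated vehicle. With self-reported eligibility, a person with a known coconut allergy could therefore meet the criteria. The frequency cannot be derived from the documents. The conclusion rests on the narrower reading of exclusion 28 and on the protocol text alone.

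Three further inferences are tempting but unsupported.
- **Misattribution.** A reader might say that a vehicle reaction would be wrongly charged to Defined CBD. As Section 6.1.1 describes it, the oil is part of the product, so recording the reaction against the product is not an error.
- **Bias or exposure in both periods.** Exposure in the placebo period is unknown, and the documents show no imbalance between treatments.
- **A precaution applied to every named ingredient.** Section 2.3.1 attaches its precautionary wording to the terpenes, and separately to the list of prohibited drugs, but not to the CBD exclusion.

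Alpha, power and the treatment estimate do not change. This is a low-frequency participant-safety improvement that the sponsor should consider; it is not a flaw in the analysis.

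**What to change.** - Reconcile Section 5.2 with the composition in Section 6.1.1: extend exclusions 28 and 29 to known allergy or hypersensitivity to any listed capsule component, naming coconut oil. Reword exclusion 28 so that its scope is unambiguous.
- Confirm that the pre-screening survey and the call script ask the matching question, and add it if they do not.
- State the placebo vehicle in Section 6.1.1, so that it is clear whether the criterion matters in one period or both.

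The cost is a phrase in Section 5.2, a sentence in Section 6.1.1, at most one added screening question, and possibly a few candidates lost. The sample size and the analysis stay as they are.
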